#### All objectives:

All analyses will be conducted separately for each database, and will be carried out in a federated manner, allowing analyses to be run locally without sharing patient-level data. A minimum cell counts of 5 will be used when reporting results, with any smaller counts reported as "<5" to comply with privacy protection regulations.

Table 11. Primary, secondary, and subgroup analysis specification.

#### A. Primary analysis

Hypothesis:	Objective 1: Not applicable, descriptive analysis.
	Objective 2: Cumulative dose and duration of treatments with NOMAC or CMA will be lower after the implementation of restrictions.
	Objective 3: The number of new users of NOMAC or CMA with prior history of meningioma will be reduced after the implementation of restrictions.
	Objective 4: The number of users initiating NOMAC or CMA as first-line treatment will be reduced after the implementation of restrictions.
	Objective 5: The number of discontinuations and switches from NOMAC or CMA to other drug classes will increase after the implementation of restrictions.
	Objective 6: The incidence of NOMAC or CMA will be reduced after the implementation of restrictions, especially for high-dose products. This reduction will not be observed for other drug classes of interest.
Exposure contrast:	Objective 1: Not applicable, descriptive analysis.
	Objective 2: Pre-intervention (1-year period) vs. Post-intervention (1-year period)
	Objective 3 to 6: Pre-intervention vs. Post-intervention
Outcome:	Objective 1: Incidence rates and prevalence of drug classes of interest
	Objective 2: Cumulative dose and treatment duration of NOMAC or CMA.

Authors: [name], [name], [name], [name], [name]

Version: V4.0

Dissemination level: Public

	Objective 3: Number and characteristics of users of drug classes of interest.
	Objective 4: Line of treatment when initiating NOMAC or CMA.
	Objective 5: Diagnosis with meningioma during treatment. Discontinuations and switches
	from treatments with NOMAC or CMA to others.
	Objective 6: Incidence rates of NOMAC or CMA.
	Drug classes of interest, NOMAC and CMA will be assessed separately.
Analytic software:	R
Model(s):	Objective 1: Not applicable, descriptive analysis.
	Objective 2 to 5: Standardised mean differences.
	Objective 6: Segmented regression (Poisson models).
Confounding adjustment method	
	Stratification.
Missing data methods	
	The absence of a record for a condition or medication will be considered as the absence of the disease or use of the medication.
Subgroup Analyses	
	Objective 1: Age groups, indication, study period. For NOMAC or CMA only: dose, WHO ATC 5 th level (if counts allow). A subgroup analysis will be performed restricting the study population to individuals with a prior history of meningioma.
	Objective 2: Study population, indication, study period.
	Objective 3: Study period.
	Objective 4: Study population, study period, exposure of interest (NOMAC vs. CMA), dose and indication.
	Objective 5: Study population, WHO ATC 5th level (if counts allow), study period, dose.
	Objective 6: Dose (high-dose products only), indication.

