### **Variables**

#### Drug classes of interest:

- Progestogen and oestrogen combination products (WHO ATC G03AA, G03AB, G03FA and G03FB)
- Progestogens that are pregnadien derivates (WHO ATC G03DB)

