#### Progestogens of interest:

- Medroxyprogesterone (WHO ATC G03AC06, G03DA02, G03AA17, G03FA12, G03FB06, G03AA08)
- NOMAC (WHO ATC G03AA14, G03DB04, G03FB12)
- CMA (WHO ATC G03AA15, G03AB07, G03DB06, G03FB03)

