## 7. RESEARCH QUESTION AND OBJECTIVES

The overall aim of the study is to describe how prescribing of NOMAC and CMA has changed following the introduction of EU-level RMM related to the risk of meningioma ('restrictions to use' from now on) in November 2022. To contextualise findings, changes of other relevant drug classes will also be described.

The specific objectives are:

- 1. To assess the monthly prevalence and incidence of use of drug classes of interest before and after the implementation of the restrictions of use.
- 2. To assess duration of use and cumulative dose of products containing NOMAC or CMA before and after the implementation of restrictions of use.
- 3. To describe characteristics of users of relevant drug classes before and after implementation of the restrictions of use.
- 4. To describe the line of treatment (2nd/3rd versus 1st) in users of products containing NOMAC or CMA before and after the implementation of the restrictions of use
- 5. To describe the frequency of patients who develop meningioma during treatment with products containing NOMAC or CMA, and those who discontinue or switch to alternative treatments before and after implementation of the restrictions of use.
- 6. To assess the impact of the restrictions of use adopted in 2018 and 2022 in incident prescriptions of products containing NOMAC or CMA.

Objective 1 and 3 will be assessed for all relevant drug classes. These will include progestogen and estrogen combination products, progestogens that are pregnadien derivates, and medroxyprogesterone-containing products.

Objective 2 and 6 will focus on products containing NOMAC or CMA. Objective 4 and 5 will focus on these two compounds but will consider relevant drug classes to establish line of treatment or switches.

A description of the proposed objectives is described in Table 1.

**Table 1.** Primary and secondary research questions and objective.

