#### Objective 6:

The impact of the restrictions of use will be estimated using an ITS. This analysis will be restricted to NOMAC and CMA (assessed separately) and will be informed by results of the main analysis obtained as part of objective 1 (no meningioma restriction). For NOMAC, the intervention taken place in 2018 will also be assessed.

Time series will be assessed using segmented regression. Monthly incident counts of patients prescribed with NOMAC or CMA will be modelled using a Poisson regression model. Quasi-Poisson models will be considered in the presence of overdispersion. The effect size of the intervention will be estimated using risk ratios (RR).

The assumption of linearity will be assessed by visually inspecting the data and residuals, as well as through statistical goodness-of-fit tests. Autocorrelation will be assessed by examining the plot of residuals and the partial autocorrelation function and conducting statistical tests where possible. If seasonality is detected, it will be controlled for by including variables representing them in the regression model. If the trends are not (or cannot be transformed to be linear) or in the presence of residual autocorrelation, ITS will not be conducted due to the complexity of predicting the counterfactual and to disentangle the intervention effects.(23)

Authors: [name], [name], [name], [name], [name]

Version: V4.0

Dissemination level: Public

The impact model of the intervention (i.e. how we expect the intervention has impacted the outcome) is anticipated to show an abrupt change in the level and a gradual change in the gradient of the trend (step and slope change). Potential impact models will be further discussed and agreed with EMA and defined a priori.(23, 24)

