# **Drug classes:**

Drug class	Analysis	WHO ATC 4 th level codes 	WHO ATC 5 th level codes 
Progestogens that are pregnadien derivates	Objective 1	G03DB	All descendants included
Progestogen and oestrogen combination products	Objective 1	G03AA, G03AB, G03FA, G03FB	All descendants included

Authors: [name], [name], [name], [name], [name]

Version: V4.0

Dissemination level: Public

		T .	I
Medroxyprogesterone 	Objective 1	N/A	G03AC06, G03DA02,
			G03AA17, G03FA12,
			G03FB06, G03AA08,
			L02AB02
Nomegestrol	Objective 1 and 6	N/A	G03AA14, G03DB04,
			G03FB12
Chloramidinone	Objective 1 and 6	N/A	G03AA15, G03AB07,
	-		G03DB06, G03FB03
Progestogen and estrogen	Objective 4 and 5	G03AA, G03AB,	All descendants
combination products not	-	G03FA, G03FB	included, except:
containing nomegestrol or			G03AA14, G03AA15,
chlormadinone.			G03AB07, G03FB12 and
			G03FB03
Progestogens that are	Objective 4 and 5	G03DB	All descendants
pregnadien derivates not			included, except:
containing nomegestrol or			G03DB04 and G03DB06.
chlormadinone.			
Drug classes of interest (any)	Objective 3	G03AA, G03AB,	All descendants
		G03DB, G03FA, G03FB	included

<sup>1 All descendants included.

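### Objective 6 expects no fall in other drug classes, but the ITS does not model them, and two of the three context series contain NOMAC and CMA themselves

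*Protocol*

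**What the plan says.** The Objective 6 hypothesis, in Table 1 (Section 7) and again in Table 11 (Section 8.8), has two parts. NOMAC or CMA incidence will fall, especially for high-dose products; and "This reduction will not be observed for other drug classes of interest".

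The Objective 6 analysis covers only the first part. Section 8.8 says of the ITS: "This analysis will be restricted to NOMAC and CMA (assessed separately". Table 11 gives the outcome as "Objective 6: Incidence rates of NOMAC or CMA", and Section 7 states "Objective 2 and 6 will focus on products containing NOMAC or CMA". Table 8 and Appendix I assign only the NOMAC and CMA series to Objective 6 by name.

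The other groups appear as monthly series in Objective 1, for which Table 11 enters "Objective 1: Not applicable, descriptive analysis" under hypothesis, contrast and model. The context groups are:

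- "Progestogens that are pregnadien derivates (WHO ATC G03DB");
- progestogen-oestrogen combinations (G03AA, G03AB, G03FA, G03FB);
- medroxyprogesterone, which Section 7 counts among the relevant classes.

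For the first two, the fifth-level entry in Appendix I is "All descendants included". Appendix I also holds versions of both classes without NOMAC and CMA, assigned to Objectives 4 and 5.

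**The concern.** The second part of the hypothesis is a specificity check. If prescribing of related products stays level while NOMAC and CMA fall, the risk minimisation measures are a more credible explanation than something affecting all hormonal prescribing. The protocol has reason to want such a check: Section 11 warns that COVID-19 effects may persist into 2021, the first year of the 2022 ITS window, and Table 11 offers only stratification against confounding.

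The check is weakened in two ways. No planned model addresses it. And the series left for an informal comparison are partly made up of the drugs under study, so a successful intervention pulls its own comparator down. That is the opposite of what the hypothesis predicts.

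**Working it through.** The plan states no figure to reproduce, and Section 8.7 says that no sample size calculation was done. The check is a code mapping, a simple formula and a look at the washout rule.

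**1. Code overlap.** Each fifth-level code is placed in its fourth-level class. The Abstract gives "NOMAC (WHO ATC G03AA14, G03DB04, G03FB12") and, for CMA, G03AA15, G03AB07, G03DB06 and G03FB03.

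| Group | In the pregnadien class | In the combination class | In neither |
|---|---|---|---|
| NOMAC (3 codes) | G03DB04 | G03AA14, G03FB12 | none |
| CMA (4 codes) | G03DB06 | G03AA15, G03AB07, G03FB03 | none |
| Medroxyprogesterone (6 codes) | none | G03AA17, G03AA08, G03FA12, G03FB06 | G03AC06, G03DA02 |

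All 3 + 4 = 7 NOMAC/CMA codes lie inside the two classes. No medroxyprogesterone code is a NOMAC or CMA code.

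**2. Size of the pull.** Let s be the NOMAC/CMA share of new use in a class, r the relative fall in NOMAC/CMA, and w the fraction of the lost starts replaced by another product of the same class. If the other products are otherwise unchanged:

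class rate ratio = 1 − s × r × (1 − w)

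The documents give none of s, r or w; all three are assumed. With w = 0:

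| s | r = 20% | r = 50% | r = 80% |
|---|---|---|---|
| 5% | 0.99 | 0.975 | 0.96 |
| 10% | 0.98 | 0.95 | 0.92 |
| 25% | 0.95 | 0.875 | 0.80 |
| 50% | 0.90 | 0.75 | 0.60 |
| 75% | 0.85 | 0.625 | 0.40 |

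These are upper limits on the pull. For s = r = 50%, w = 0.5 gives 1 − 0.25 × 0.5 = 0.875, and w = 1 gives 1.00. With NOMAC and CMA removed from the class and no change elsewhere, the ratio is 1.00 by construction.

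**3. Can the reader subtract?** Not for incidence. Sections 8.4 and 8.8 apply the 365-day washout to each outcome separately. A woman who moves from another G03DB product to NOMAC within the washout is a new user of NOMAC but not of G03DB. Class incidence minus NOMAC and CMA incidence is therefore not the incidence of the remaining products. The NOMAC and CMA series also each span both classes, and the fifth-level breakdown that would separate them is promised only if counts allow.

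**4. Post-intervention months at the data locks in Table 3.** The post period starts in February 2023, and Section 11 drops the last six months for the two IQVIA sources in Objectives 1 and 6.

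- Germany: lock 30 September 2023, usable to March 2023, 2 months.
- Belgium: lock 31 December 2023, usable to June 2023, 5 months.

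This limits what any model of the comparator series could show, unless the data are refreshed.

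**The case against.** The strongest reply is that the other classes are there for context. The overall aim says so, Objective 1 is openly descriptive, and Section 8.6 discloses that some progestogens of interest sit inside the classes. NOMAC and CMA have their own monthly series, so a reader sees their fall beside the class series. Medroxyprogesterone is an uncontaminated series, reported monthly with confidence intervals. Section 8.4 also mentions Objectives 1 and 6 together when it says that drug classes are assessed separately.

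Much of this stands. An informal comparison is available, and it is wrong to say that the hypothesis cannot be examined at all. But disclosing an overlap does not remove it, and step 3 shows that the reader cannot undo it. Medroxyprogesterone is a weak sole comparator because Section 6 says it has itself been linked to meningioma. The remark in Section 8.4 concerns washout and does not override the explicit restriction in Section 8.8.

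Four stronger readings are tempting and are not supported:

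- A reader might infer that every context series is contaminated. Medroxyprogesterone is not.
- A reader might infer that the lists without NOMAC and CMA serve only Objectives 4 and 5. That holds for their use as outcomes; Section 8.6.3 and Table 9 also use those groups as concomitant medications in Objective 3.
- A reader might infer that the protocol itself names panel turnover or general shifts in hormonal prescribing as threats. It names COVID-19 and an end-of-data denominator artefact, and calls the Belgian panel stable.
- A reader might infer that a class-wide fall would be taken as evidence against the measures. That is possible, but speculative with the separate series alongside.

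**Conclusion.** The point holds in a limited form. The second part of the Objective 6 hypothesis has no formal analysis, and two of the three series available for an informal one include all seven codes of the drugs under study. The direction follows from the code lists alone: a NOMAC/CMA fall lowers those class series unless substitution within the class offsets it. The size is unknown. It is at most share times fall, and can be zero with full substitution; the tabulated ratios of 0.99 to 0.40 rest on assumed shares of 5% to 75%, assumed falls of 20% to 80% and no substitution.

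The NOMAC and CMA estimates themselves are unaffected. A reader might infer that a controlled ITS, with a ratio of level changes, is therefore required. The documents do not support that: switching away from NOMAC and CMA can raise the comparator and exaggerate such a ratio, and two or five post-intervention months in the IQVIA sources would make it very imprecise.

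**What to change.** 1. In Objective 1, report monthly incidence and prevalence of both classes on the Appendix I code lists that leave out NOMAC and CMA. Keep the full class as an extra row. Add Objective 1 to the entries for those lists in Table 8 and Appendix I.

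2. Then bring hypothesis and analysis into line, in one of two ways:
   - fit the same segmented model to the two clean series as a secondary comparison, shown beside the NOMAC and CMA estimates, with a note that switching can raise these series and that few post-intervention months are available; or
   - reword the second sentence of the Objective 6 hypothesis in Tables 1 and 11 as a descriptive expectation, assessed in Objective 1.

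The cost is small. The code lists exist, so step 1 adds two outcomes to the incidence and prevalence runs. The modelling option adds further runs of a model already planned; the rewording option changes one sentence in two tables.

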## 8.9 Evidence synthesis

Results from analyses described in section 8 will be presented separately for each database and no metaanalysis of results will be conducted.

Authors: [name], [name], [name], [name], [name]

Version: V4.0

Dissemination level: Public

## 9. DATA MANAGEMENT

#### Data management

All databases are mapped to the OMOP CDM. This enables the use of standardised analytics and tools across the network since the structure of the data and the terminology system is harmonised. The OMOP CDM is developed and maintained by the Observational Health Data Sciences and Informatics (OHDSI) initiative and is described in detail on the wiki page of the CDM:

https://ohdsi.github.io/CommonDataModel and in The Book of OHDSI: http://book.ohdsi.org.

The analytic code for this study will be written in R. Each data partner will execute the study code against their database containing patient-level data and will then return the results set which will only contain aggregated data. The results from each of the contributing data sites will then be combined in tables and figures for the study report.

#### Data storage and protection

For this study, participants from various European Union member states will process personal data from individuals which is collected in national/regional electronic health record databases. Due to the sensitive nature of this personal medical data, it is important to be fully aware of ethical and regulatory aspects and to strive to take all reasonable measures to ensure compliance with ethical and regulatory issues on privacy.

All databases used in this study are already used for pharmaco-epidemiological research and have a well-developed mechanism to ensure that European and local regulations dealing with ethical use of the data and adequate privacy control are adhered to. In agreement with these regulations, rather than combining person level data and performing only a central analysis, local analyses will be run, which generate non-identifiable aggregate summary results.

## 10. QUALITY CONTROL

### General database quality control

Several open-source quality control mechanisms for the OMOP CDM have been developed (see Chapter 15 of The Book of OHDSI http://book.ohdsi.org/DataQuality.html). In particular, data partners are expected to run the OHDSI Data Quality Dashboard tool

(https://github.com/OHDSI/DataQualityDashboard). This tool provides numerous checks relating to the conformance, completeness and plausibility of the mapped data. Conformance focuses on checks that describe the compliance of the representation of data against internal or external formatting, relational, or computational definitions, completeness in the sense of data quality is solely focused on quantifying missingness, or the absence of data, while plausibility seeks to determine the believability or truthfulness of data values. Each of these categories has one or more subcategories and are evaluated in two contexts: validation and verification. Validation relates to how well data align with external benchmarks with expectations derived from known true standards, while verification relates to how well data conform to local knowledge, metadata descriptions, and system assumptions.

#### Study specific quality control

Concepts and phenotypes of interest will be developed and assessed using the following R packages: "CodelistGenerator", "CohortDiagnostics" and "DrugExposureDiagnostics". The study code will be based on different R packages to: 1) estimate incidence rates and period prevalence ("IncidencePrevalence"), 2) characterise patients "PatientProfiles" and "CohortCharacteristics") and 3) summarise patient-level drug

P3-C3-006 Stud	v Protoco
----------------	-----------

Authors: [name], [name], [name], [name], [name]

Version: V4.0

Dissemination level: Public

use ("DrugUtilisation"). These packages will include numerous automated unit tests to ensure the validity of the codes, alongside software peer review and user testing.

# 11. LIMITATIONS OF THE RESEARCH METHODS

#### General limitations:

The study will be informed by routinely collected health care data and so data quality issues inherent to observational studied need to be considered. As such, the recording of events (e.g. comorbidities, medications) may vary across databases and might be inaccurately recorded or incomplete. In addition, results will only reflect events occurring in the healthcare settings covered by each database, and therefore prescriptions issued outside the healthcare institutions covered by each data partner will not be captured.

#### **Databases:**

In IQVIA LPD Belgium and IQVIA DA Germany, the observation period of the patients in these databases is calculated based on the last visit, observation or interaction of the patient with the health care system. This methodology impacts the individuals considered "at risk" for the different medicines of interest of the study (i.e., the individuals included in the denominator populations) during the latest months of available data from the latest data lock, where healthy and/or non-frequent users of the health care system will not be considered active. Consequently, the denominators that will be used to calculate the incident use of drugs in the population may present an artefactual decrease whilst the incident users will remain, incrementing the incidence and prevalence ratios. The presence of these artefacts will be considered when interpreting the results. However, this is likely to affect the amount of follow up available for the study. We expect that the data from the last 6 months may not accurately reflect actual figures of use and, therefore, will be excluded from the analysis for Objective 1 and 6.

Regarding the study period, NAJS will provide data from 2017 onwards only, as prior data might include information on duplicated patients. IQVIA LPD Belgium will provide data from 2012 onwards.

Since information on drug exposure end dates is unavailable in NAJS, treatment duration will not be inferred directly from the start and end dates of drug exposure. Instead, we will infer the treatment period using only the drug exposure start dates, assuming continuous drug exposure between consecutive start dates, if separated by less than 90 days. To account for the final prescription, we apply a 30-day window following the last recorded drug start date. This approach might lead to some uncertainty regarding the exact duration or cumulative dose prescribed.

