## 8.4 Follow-up

For the population-level DUS (objective 1), study participants in the denominator population will start contributing person time on the latest of the following: 1) study start date (1st January 2010, or as defined according to the database), 2) date on which they turn 10 years old, 3) date at which they have a year of prior history recorded. Participants will stop contributing person time at the earliest date of the following: 1) end of available data in each of the data sources, 2) date at which their observation period ends (e.g. loss to follow-up, death).

For the patient-level DUS (objective 2 to 5), participants will be followed up from the day of incident prescription of medication (index date), until the earliest end of data availability, date at which their observation period ends (e.g. loss to follow-up, death), or 180 days after ending treatment (objective 5). For objective 2, 4 and 5, index date will be defined as the date of the first-ever prescription of NOMAC or CMA. For objective 3, this will be defined as the date of the first-ever prescription of any of the 6 drug classes of interest (see "8.6.2 Outcomes").

For objective 4, line of treatment will be assessed retrospectively by looking at prior records of alternative treatments, from the date of initiation of treatment with products containing NOMAC or CMA to start of the study period (1st January 2010, or as defined according to the database).

For objective 6, follow-up will be the same as that for objective 1.

Information on the operational definition of index date is described in **Table 4**. Please note that, for objectives 1 and 6, each drug class of interest will be assessed separately, with the washout window specific to the drug class being studied (e.g., when studying NOMAC, the washout window will be applied with respect to this substance only). For objective 3, the washout will be applied to all the drug classes of interest combined.

Authors: [name], [name], [name], [name], [name]

Version: V4.0

**Dissemination level:** Public

Table 4. Operational definition of time 0 (index date) and other primary time anchors.

Study population names	Time Anchor Description (e.g. time 0) 	Number of entries 	Type of entry	Washout window	Care Setting 	Code Type 	Incident with respect to

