## Objective 2:

Treatment duration will be reported for the first prescribed treatment. Duration will be derived from the start and end of the prescription.

Cumulative dose will be calculated considering all treatments containing NOMAC or CMA recorded during the study period. If two eras with different doses are separated by less than 30 days, the time between the two eras will be considered as exposed by the first era (Figure 1, first row). If two eras start at the same date, the overlapping period will be considered exposed by both.

[figure not shown]

Figure 1. Gap era joint mode

Cumulative dose and treatment duration will be calculated for all treatments initiated during the study period and occurring over one year before and after the intervention to compare time periods of equal duration. The pre-intervention period for comparison will span from October 2021 to September 2022,

Authors: [name], [name], [name], [name], [name]

Version: V4.0

Dissemination level: Public

the year prior the request for PRAC to review current evidence on NOMAC and CMA. The post-intervention period for comparison will span from February 2023 to January 2024. For databases with less available data (see Table 3) we will limit the comparison to 6 months (post-intervention: February to July 2023; pre-intervention: February to July 2022). Time periods for comparison will cover the same calendar months in case seasonality is detected.

NOMAC and CMA will be assessed separately. Results will be reported overall and stratified by study period (pre- vs. postintervention) and indication at first use (non-HRT vs. HRT).

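### Sections 8.4 and 8.8 end Objective 2 treatment time differently in the two IQVIA databases; if 8.4 governs, duration and dose are shortened more after the restrictions than before

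*Protocol*

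**What the plan says.** - **Observation rule (section 11, Databases).** For both IQVIA sources, "the observation period of the patients in these databases is calculated based on the last visit, observation or interaction of the patient".
- **Correction (same paragraph).** The sponsor writes "We expect that the data from the last 6 months may not accurately reflect actual figures of use", and those months "will be excluded from the analysis for Objective 1 and 6". The reason given is a shrinking denominator. Treatment length is not discussed.
- **Follow-up (section 8.4).** New users in Objectives 2 to 5 are followed "until the earliest end of data availability, date at which their observation period ends". Objective 2 is not exempted.
- **Duration (section 8.8, Objective 2).** "Duration will be derived from the start and end of the prescription". Nothing is said about cutting that end date when observation stops.
- **Windows (section 8.8, Objective 2).** The standard rule is one year: "The post-intervention period for comparison will span from February 2023 to January 2024", set against October 2021 to September 2022. Databases with less data use six months: "post-intervention: February to July 2023; pre-intervention: February to July 2022".
- **Locks (Table 3).** 30 September 2023 for Germany and 31 December 2023 for Belgium.
- **Hypothesis and measures (Tables 1 and 11).** Duration and cumulative dose are expected to be lower after the restrictions. They are reported as a median with quartiles and range, and compared by standardised mean difference (SMD).

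**The concern.** Duration and cumulative dose are the whole of Objective 2. If a prescription stops counting at the woman's last recorded contact, supply that runs beyond that contact is lost. Women who started shortly before the lock have had less time to make another contact, so they lose supply more often. The post-restriction window lies close to the lock and the pre-restriction window more than a year further away. Matching calendar months deals with seasonality and does nothing about distance to the lock. The resulting fall would point the same way as the hypothesis and could be read as an effect of the restrictions with no change in prescribing.

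**Working it through.** The protocol gives no figure of its own to reproduce here.

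**1. The two rules for one woman (illustration).** A German starter receives an assumed 84-day prescription on 15 June 2023, 107 days before the lock, and has no later contact. By 8.8 her duration is 84 days. By 8.4, with observation ending at that contact, it is about one day.

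**2. Distance from start to the listed lock (dates from 8.8 and Table 3).**

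| Database and window | Post, days to lock | Pre, days to lock | Post-window days in last six months | Pre-window days in last six months |
|---|---|---|---|---|
| Germany, 6 months | 61–241 | 426–606 | 122 of 181 (67%) | 0 |
| Belgium, 6 months | 153–333 | 518–698 | 31 of 181 (17%) | 0 |
| Belgium, 12 months cut at lock | 0–333 | 457–821 | 184 of 334 (55%) | 0 |

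For Germany, April to July 2023 is 30 + 31 + 30 + 31 = 122 days.

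**3. Share whose first prescription falls on the last recorded contact.** Share = q + (1 − q) × mean[exp(−T/g)], where T is days to lock (uniform over the window), g the mean gap between contacts and q the share who never return. The documents give neither g nor q.

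Germany with g = 90 days and q = 10%:
- Post: mean = (90/180) × (e^(−61/90) − e^(−241/90)) = 0.5 × (0.508 − 0.069) = 0.220. Share = 0.10 + 0.90 × 0.220 = 30%.
- Pre: mean = 0.5 × (e^(−426/90) − e^(−606/90)) = 0.004. Share = 10%.

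| Window | Post, g 60–180 days, q 10–30% | Pre, same inputs | Ratio | Ratio at g = 30 days |
|---|---|---|---|---|
| Germany, 6 months | 20–62% | 10–34% | 1.3–3.3 | 1.1–1.2 |
| Belgium, 6 months | 12–49% | 10–32% | 1.1–2.6 | 1.0 |
| Belgium, 12 months | 26–62% | 10–32% | 1.4–3.9 | 1.2–1.8 |

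**4. Effect on recorded duration of the first prescription.** Simulation with 400,000 women per setting and no true change. Assumed: 28- or 84-day supply; 30 or 50% receive only one prescription and the others refill on time; other contacts occur at random. Recorded duration = min(supply, days to lock, days to last contact + 1). SMD = (post mean − pre mean) / √((post variance + pre variance)/2). Six-month windows.

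| Database | Other contacts a year | Fall in mean | SMD |
|---|---|---|---|
| Germany | 1 to 4 | 7–34% | about −0.4 to −0.9 |
| Germany | 12 | about 1–9% | −0.16 to −0.58 |
| Belgium | 1 to 4 | 3–20% | −0.24 to −0.55 |
| Belgium | 12 | under 1% | −0.04 to −0.10 |

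One German example (84 days, 2 contacts a year, 50% single prescriptions): the mean falls from 80.7 to about 55.5 days. The median was 28 or 84 days, unchanged, in every setting. The lower quartile fell in some; in this example it went from 84 days to 1.

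**5. Prescription's own end date, cut only at the lock.** The post/pre ratio of means is 0.98 for 84-day supply in Germany and 1.00 otherwise. The 0.98 comes from July starters whose supply runs past 30 September 2023.

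**The case against.** The best defence is that 8.8 already gives the rule. It takes duration from the prescription's start and end. Section 11 says this cannot be done directly in the Croatian data because end dates are missing there, which implies that it is done in the IQVIA data. Section 8.4 is a general follow-up rule and does not say that a recorded end date is pulled back to the last contact. The six-month exclusion was aimed at rates with a population denominator, which Objective 2 does not have. The planned median did not move. The locks are those of the last update listed, while the code is to run in March/April 2025, so a later extract may be used.

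Most of this limits the point without removing it. On the literal 8.8 reading the artefact all but disappears. But 8.4 covers Objective 2 without exception, and no sentence says which rule prevails. The Croatian data have an explicit rule for the final prescription (a 30-day window after the last start); the IQVIA data have none. The SMD is also a planned measure, and it does move.

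A reader might infer that last-visit prescriptions will count as one day, and far more often after the restrictions. The documents do not support that as fact. No passage states it, and the frequency rests on contact rates that the protocol does not give.

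**Conclusion.** The inconsistency between 8.4 and 8.8 is real and needs to be reconciled. The bias is conditional: it arises only if observation end cuts the prescription. It then acts in the hypothesised direction on the SMD, possibly on the lower quartile, and not necessarily on the median.

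The distances to the lock follow from the documents. The size does not: it depends on contact frequency, supply length, the share who never return and the lock finally used. Under the assumed 1 to 4 contacts a year it would be material in Germany and smaller in Belgium with six-month windows; with monthly contacts it is modest or negligible. The simulated SMDs also assume one supply length for all women. A mix of lengths would widen the spread and reduce them.

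**What to change.** State in 8.4 and in 8.8 (Objective 2) that in IQVIA DA Germany and IQVIA LPD Belgium both duration and cumulative dose count each prescription to its own recorded end date, not cut at the last contact and truncated only at the database lock. Limit both comparison windows to the same calendar months whose first supply can end before the lock actually used. With the listed German lock and 84-day supply, that means February to June.

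The cost is a sentence in each section, a code setting, and about one month fewer of German starters in each window. This keeps far more data than extending the six-month exclusion to Objective 2, which would leave 59 of the 181 German post-window days. It does not equalise the time in which further prescriptions can accumulate towards cumulative dose; that is a separate matter.
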